10.4 Analysis of Vital Signs

Vital sign measurements of systolic and diastolic blood pressure, pulse rate, body weight, respiratory rate and body temperature will be summarized.

Each vital sign variable will be summarized for all time points (starting with Baseline) with the number of non-missing observations, mean and standard deviation, median, minimum and maximum. Mean change from Baseline to each applicable post-baseline visit will be summarized for each vital sign variable, with the number of observations, Baseline mean, and visit mean. The change from Baseline mean, standard error, and 95% CI will be presented for the mean change from Baseline within each treatment group.

For SA1 population, treatment group differences between upadacitinib group and placebo group for changes from Baseline will be analyzed using a one-way Analysis of Variance

(ANOVA) with treatment as a fixed factor and 95% CI for treatment difference will be presented for each vital sign variable.

Vital sign variables will be evaluated based on potentially clinically important (PCI) criteria ([Appendix C](#)). For each vital sign PCI criterion, the number and percentage of subjects who have a vital sign value meeting the criteria will be summarized. Listings will be provided to summarize subject-level vital sign data for subjects meeting PCI criteria.

11.0 Interim Analyses

There will be no efficacy interim analyses planned for this study.

11.1 Data Monitoring Committee

An external data monitoring committee (DMC) composed of persons independent of AbbVie and with relevant expertise in their field will review unblinded safety data from the ongoing study. The primary responsibility of the DMC will be to protect the safety of the subjects participating in this study.

A separate DMC charter describes the roles and responsibilities of the DMC members, frequency of data reviews, relevant data to be assessed, and general operations.

Since there are no efficacy analyses for early stopping, no alpha adjustment is needed.

12.0 Overall Type-I Error Control

The overall type I error rate of the co-primary and ranked secondary endpoints will be strongly controlled using a fixed sequence multiple-testing procedure¹ as well as Holm procedure⁵ as described below. Specifically, the testing will utilize the sequence of hypothesis testing for the co-primary endpoints followed by a set of ranked key secondary endpoints (Group 1A_E for EU/EMA, Group 1A_F for US/FDA) in the order as specified in Section 3.2, and will begin with testing each of the co-primary endpoints using two-sided α of 0.05. If both of the co-primary endpoints are statistically significant at

two-sided 0.05 level of significance, the Group 1A (Group 1A_E for EU/EMA, Group 1A_F for US/FDA) ranked secondary endpoints will be tested at two-sided α of 0.05 in the order specified in Section 3.2. If the co-primary endpoints and the Group 1A (Group 1A_E for EU/EMA, Group 1A_F for US/FDA) ranked secondary endpoints are statistically significant at two-sided 0.05 level of significance, the Group 1B (Group 1B_E for EU/EMA, Group 1B_F for US/FDA) ranked secondary endpoints will be tested using the Holm procedure at two-sided α of 0.05. The graphs for the testing procedures are provided in [Figure 3](#) (for EU/EMA regulatory purpose) and [Figure 4](#) (for US/FDA regulatory purpose).

Figure 3. Graphical Multiple Testing Procedure for Co-Primary and Ranked Secondary Endpoints for EU/EMA

[figure not shown]
[figure not shown]

Figure 4. Graphical Multiple Testing Procedure for Co-Primary and Ranked Secondary Endpoints for US/FDA Graphical Multiple Testing Procedure for Co-Primary and Ranked Secondary Endpoints for US/FDA

13.0 Version History

Table 4. SAP Version History Summary

Version	Date	Summary
1.0	05 Oct 2017	Original version
2.0	29 Jan 2018	
 • Clarification provided on Part 1 efficacy endpoints; specified Part 2 and Part 3 efficacy endpoints (Section 4.3). • Modified the graphical testing procedure to incorporate Holm procedure for the Group 1B endpoints in place of Hochberg procedure (Section 4.6). • Race and Region subgroup categories added. Details and clarification added for subgroup analyses (Section 5.2). • Specified the primary analysis for inference purposes for the continuous secondary efficacy endpoints (Section 6.3).
3.0	28 Jan 2021	
 • Revised the SAP per the latest SAP template. • The following changes have occurred in order to reflect changes in the protocol amendment and regulatory guideline. 
 ○ Updated study design based on protocol amendments to reduce the number of subjects planned for open-label induction Part 2 (from 360 to 150) ○ Updated co-primary endpoint and ranked secondary endpoints to address agency requests and reflect updates in protocol amendments ○ Added NRI-C method for handling missing data due to COVID-19. NRI-C will be used for the primary efficacy analysis and NRI-NC will be considered as sensitivity analysis ○ Removed the Last Observation Carried Forward (LOCF) approach from the missing data imputation as LOCF potentially can result in a biased estimation of treatment effect and underestimate the variability • Added definitions of estimand for primary and key secondary endpoints.

Table 4. SAP Version History Summary (Continued)

Version	Date	Summary
4.0	23 Jul 2021	
 • Add premature withdrawal from the study as an intercurrent event. • Replace Pattern Mixture Model (PMM) with tipping point analysis as the sensitivity analyses for all primary and key secondary endpoints. • Update the cutoff of CGHAS/IGHAS histology remission endpoint (defined as CGHAS/IGHAS score ≤ 2) where cutoff is updated from "≤ 3" to "≤ 2" to align with published literature (Section 3.3.1/ Section 3.3.2). • Update criteria of liver function assessment from "\geq" to "$>$" (Section 10.3). • Add and define SA4 population (Section 4.0) and corresponding TEAE for the safety analysis (Section 10.2.1) in subjects who took upadacitinib in both 12-Week Induction Period and Extended Treatment Period • Add three Other Efficacy Endpoints (Section 3.3) on clinically meaningful improvements in FACIT-F • Add details of calculation of total patient year in the exposure adjusted AE analysis (Section 10.2.4) • Delete "endoscopic remission at Week 12 among subjects with SES-CD subscore of 3 in the narrowing component at Week 12, which was not present at Baseline" (result in 0% remission rate) and "endoscopic remission or endoscopic response at Week 12 among subjects with SES-CD subscore of 3 in the narrowing component at Week 12, which was not present at Baseline" as they are not applicable by definition • Replace ANCOVA-C with ANCOVA as ANCOVA is valid under MAR missingness (Section 9.2.2) • Corrected typo on the TEAE definition for SA-UPA population (update "40 days" to "30 days," Section 10.2.1)

Table 4. SAP Version History Summary (Continued)

Version	Date	Summary
5.0	15 Nov 2021	
 • Based on FDA guidance (E9(R1) addendum Revision 1, May 2021), removed study withdrawal from the scope of intercurrent events (Section 2.1, Section 8.0, Section 9.3.2 Table 1, Section 9.4.1 Table 2) • Added a sensitivity analysis to the primary endpoints in Section 9.3.3 per agency request, and provide details on derivation of total CDAI score, average daily SF/AP (Section 3.0, Appendix D) • Add five Other Efficacy Endpoints (Section 3.3.1, Section 3.3.3) on in (1) change in FACIT-F at Week 4 and Week 12; (2) resolution of EIM at Week 2, Week 4, Week 8 and Week 12; (3) achievement of CR-100 at Week 16, Week 20 and Week 24; (4) time to CR-100; (5) achievement of endoscopic response at Week 24. • Provided more clarity that baseline characteristics will also be summarized for ITT2 (Section 7.0) • Clarified intercurrent event handling strategies (Section 8.1 and Section 8.2) • Updated the category for Race to adhere with CDISC controlled terminology, and corrected a typo in the Baseline SES-CD variable (update "$\leq 15, > 15$" to "$< 15, \geq 15$") in subgroup analysis (Section 7.1, Section 9.6 Table 3) • Provided more clarity on the concomitant medication definition (Section 7.3) • Provided more clarity on the scope of summary statistics for the Extended Treatment Period (Section 9.1) • Provided more clarity on handling premature discontinuation of study drug intercurrent event in NRI-C analysis (Section 9.2.1) • Provided more clarity on the analyses for time to response endpoints (Section 9.5) • Add sensitivity analyses on additional efficacy endpoint of change from Baseline in average daily total stool frequency (Section 9.5). • Provided more clarity on the TEAE definition, and also the scope of AE overview (Section 10.2.1, Section 10.2.2)

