### **Endoscopy**

An endoscopy (ileocolonoscopy) will be performed as specified in [Appendix C](#). It is expected that all subjects who remain in the study through at least Week 8 will have a Week 12/PD endoscopy in Part 1 or Part 2. For subjects entering Part 3, it is expected that all subjects who remain in the study through at least Week 20 will have a Week 24/PD endoscopy. An endoscopy performed before the Screening visit, independently of the study, may be used as the Screening endoscopy, with the approval of the AbbVie TA MD, if the following conditions are met:

1. Biopsy confirmation of the diagnosis is available according to section "Biopsy During Endoscopy" below, as applicable.
2. The endoscopy took place within 45 days prior to Baseline visit.
3. The endoscopy was recorded in a video format as the endoscopic eligibility will be determined by the central reviewers.

The same endoscopist, where possible, should perform all endoscopies. In addition, where possible, the investigator or sub-investigator should be the endoscopist for the study.

During the COVID-19 or any pandemic, the Week 12 and Week 24 endoscopies may be performed within 7 days of the planned date if travel restrictions or other pandemic-related reasons impact scheduling. If the endoscopy cannot be performed at the study site, it can be completed at a different hospital/facility.

If the COVID-19 or any pandemic precludes a subject from undergoing an endoscopy at:

- Week 12 or Week 24 and clinical response was achieved, the subject can enroll in Study M14-430.
- Week 12 and clinical response was not achieved, the subject can enter Part 3 of Study M14-431.

All ileocolonoscopies will be performed and recorded at the site in a video format. Sites should also perform the SES-CD assessment and record the findings on the SES-CD score sheet [Appendix J](#) and in the appropriate eCRF.

All endoscopies will be reviewed by a central reviewer who is blinded.

There will be a window of 7 days prior to the scheduled visit to conduct the endoscopy, with the exception of the screening endoscopy. This window may be extended as necessary after consultation with the AbbVie TA MD in case of external, not subject-related circumstances (e.g., scheduling conflict).

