8.1 Intercurrent Event 1 (IE1): Premature Discontinuation of Study Drug

Following the intent-to-treaty (ITT) principle, a treatment policy strategy will be used to handle the IE1. Data collected on/after premature discontinuation of study drug will be used for all efficacy endpoints.

The only exception is when data are collected on/after the date subjects switching to other treatment for CD, which will be handled as follows:

- **Binary endpoints other than the occurrence of hospitalization and/or the occurrence of CD-related surgery endpoints:** A composite strategy will be used in the efficacy analysis: the subject will be considered as non-responders at all visits on/after the initiation of other CD-related confounding medications.
- **Binary endpoints regarding the occurrence of hospitalization and/or the occurrence of CD-related surgery endpoints:** A treatment policy strategy will be used regardless.
- **Continuous endpoints:** A hypothetical strategy will be used in the efficacy analysis. Data collected on/after the initiation of other CD-related confounding medications will not be used in the analysis. Efficacy analysis will be handled by using corresponding statistical models (e.g., the Mixed-Effect Model Repeated Measurement [MMRM] model).

The CD-related confounding medications include:

- Biologics approved for CD (Adalimumab, Certolizumab, Infliximab, Ustekinumab, Vedolizumab, Natalizumab)
- Any investigational compound
- Systemic corticosteroids or locally acting steroids, rectal corticosteroid
- Immunosuppressants (azathioprine, mercaptopurine, methotrexate, tacrolimus, cyclosporine)

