Binary endpoints regarding the occurrence of hospitalization and/or the occurrence of CD-related surgery endpoints: A treatment policy strategy will be used regardless.

Continuous endpoints: A hypothetical strategy will be used in the efficacy analysis. Data collected on/after the initiation of CD-related corticosteroids will not be used in the analysis. Efficacy analysis will be handled by using corresponding statistical models (e.g., the Mixed-Effect Model Repeated Measurement [MMRM] model).

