9.2 Handling of Missing Data

Missing data could occur due to various reasons, including missing visits/assessments, early withdrawal from the clinical trials, or missing due to COVID-19 infection or logistic restrictions during the pandemic. Assessments on or after any intercurrent event will be handled as specified in Section 8.0.

The COVID-19 pandemic is interfering with the conduct of many ongoing trials, with potential impacts on treatment duration and the collection, analysis, and the interpretation of clinical trial data. For example, some scheduled visits may be missed due to self-quarantine or local government restrictions on travel; some visits may also be delayed

or canceled due to healthcare resource constraints during the pandemic. Impacted visits due to COVID-19 will be recorded in the database. The probability of having missed visits and missing data due to COVID-19 infection or logistical restrictions related to the COVID-19 pandemic can be reasonably assumed to be unrelated to the unobserved values. Therefore, for the purpose of statistical analysis, it is reasonable to assume that these missing data are missing at random (MAR) and the statistical models that require MAR assumption are appropriate. The intent is to provide reliable estimates of the treatment effects under the scenario without the impact of COVID-19 pandemic.

Missing data for the efficacy analyses will be handled using the methods described below.

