9.2.2 Continuous Endpoints

For continuous efficacy endpoints where Mixed-Effect Model Repeat Measurement (MMRM) analysis or Analysis of Covariance (ANCOVA) is performed, missing data will be handled using the following approaches.

- MMRM: The repeat measurement analysis will be conducted using a mixed model including observed measurements at all post-baseline visits up to the end of the analysis period. The mixed model includes the categorical fixed effects of treatment, visit and treatment-by-visit interaction, stratification factors at randomization, and the continuous fixed covariates of baseline measurement. An unstructured variance covariance matrix will be used. If the model cannot converge, an appropriate variance-covariance structure matrix (e.g., autoregressive or compound symmetry) will be used. Parameter estimation is based on the method of restrictive maximum likelihood (REML). MMRM will

be the primary approach in the analysis of continuous variables with repeated measurements.

- ANCOVA: For continuous efficacy variables that are collected at only one post-baseline visit (such as SES-CD), ANCOVA will be used. The model includes the categorical fixed effects of treatment, stratification factors at randomization, and the continuous fixed covariates of baseline and measurement.

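### The observed-case ANCOVA for change in SES-CD may be biased if endoscopies are lost through treatment failure, and the stated MAR reason does not cover that loss

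*SAP*

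**What the plan says.** Change from baseline in SES-CD at Week 12 is one of the other Part 1 endpoints in SAP 3.3.1. SAP 4.0 assigns it to ITT1, and SAP 9.1 tests it at two-sided 0.05 without multiplicity adjustment.

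- Model (SAP 9.2.2): "For continuous efficacy variables that are collected at only one post-baseline visit (such as SES-CD), ANCOVA will be used". Its terms: "The model includes the categorical fixed effects of treatment, stratification factors at randomization, and the continuous fixed covariates of baseline and measurement". The last words are read here as the baseline measurement. The model has no post-baseline variable and no imputation step.
- Values kept and discarded: SAP 8.1 says "Data collected on/after premature discontinuation of study drug will be used for all efficacy endpoints". After a switch to other Crohn's treatment, however, the rule for continuous endpoints is "Data collected on/after the initiation of other CD-related confounding medications will not be used in the analysis". SAP 8.2 adds, for the corticosteroid event, "Data collected on/after the initiation of CD-related corticosteroids will not be used in the analysis". Both sections leave the consequence to the statistical model, with MMRM as the example.
- Who is scoped (Protocol 5.3.1.1, Endoscopy): "It is expected that all subjects who remain in the study through at least Week 8 will have a Week 12/PD endoscopy".
- Reason given (SAP 13.0, Version 4.0): "Replace ANCOVA-C with ANCOVA as ANCOVA is valid under MAR missingness". The only argument for MAR in the body of the SAP is in 9.2 and concerns the pandemic: "missing data due to COVID-19 infection or logistical restrictions related to the COVID-19 pandemic can be reasonably assumed to be unrelated to the unobserved values".

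**The concern.** A subject without a usable Week 12 SES-CD contributes nothing to this ANCOVA, although the analysis set is ITT1. In effect the analysis is observed-case. It is not the SAP's AO analysis, which keeps values recorded after intercurrent events.

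MAR allows missingness to depend on anything observed, including symptoms and CRP at Weeks 2 to 8. An ANCOVA on treatment, strata and baseline needs more: given those terms alone, missingness must be unrelated to the outcome. Several routes to loss in this plan follow post-baseline events: leaving before Week 8 (Protocol 5.4.1 lists lack of response among the reasons for leaving), switching therapy, or a corticosteroid event.

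For IBDQ and FACIT-F, MMRM can draw on the Week 4 value. SES-CD has no earlier post-baseline value to draw on. For endoscopic response, NRI-C keeps the same subjects as non-responders; for SES-CD change they disappear. At stake are the size and confidence interval of the only continuous endoscopic result in Part 1.

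**Working it through.** 1. The plan's own figure. The documents give no effect size, SD, loss rate or power for SES-CD change. The nearest endoscopic figure is in SAP 2.4: endoscopic response 10% vs 25%, 165 vs 330 subjects, Fisher's exact test, two-sided 0.05, power at least 95%. Recomputed, power is 98.7% by exact enumeration and 98.8% by the pooled z formula. The figure reproduces, but this point does not depend on it.

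2. Inputs. From the documents: 330 and 165 subjects, the ANCOVA terms and the routes to loss. Assumed: residual SD 1; true difference −0.50 SD; correlation ρ of 0 to 0.6 between post-baseline course and Week 12 change, given arm and baseline; 8–30% lost on placebo and 5–15% on upadacitinib. The strata are left out of the simulation.

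3. Model. T = 1 for upadacitinib, B is standardised baseline, Z is a post-baseline symptom score (higher is worse), Y is the SES-CD change (negative is better), and e and u are independent standard normal.

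- Y = −0.5T − 0.5B + ρe + √(1 − ρ²)u
- Z = −0.5T − 0.2B + e
- Loss after failure: logit P(lost) = c + 2Z, with c set in each arm to give the stated loss
- Comparison case: logit P(lost) = c + B, so loss depends on arm and baseline only

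4. Source of bias. With B held fixed, the mean of Y among subjects kept in an arm shifts by ρ times their mean e. So bias ≈ ρ × G, where G is mean e among kept upadacitinib subjects minus mean e among kept placebo subjects. G is zero when selection is equal and positive when placebo loses more failures.

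5. Bias of the observed-case ANCOVA in SD units (400,000 placebo and 800,000 upadacitinib subjects; positive means attenuated):

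| Loss, placebo/upadacitinib | ρ = 0.2 | ρ = 0.4 | ρ = 0.6 | G = bias/ρ at ρ = 0.6 |
|---|---|---|---|---|
| 10%/5% | +0.012 | +0.025 | +0.040 | 0.040/0.6 = 0.07 |
| 20%/8% | +0.028 | +0.055 | +0.087 | 0.087/0.6 = 0.145 |
| 30%/12% | +0.041 | +0.084 | +0.123 | 0.123/0.6 = 0.205 |
| 15%/15% | −0.001 | −0.002 | −0.001 | 0.00 |
| 8%/15% | −0.016 | −0.034 | −0.052 | −0.052/0.6 = −0.09 |

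With ρ = 0, bias is within 0.001. With loss depending on arm and baseline only, it is within 0.003. Across the 20%/8% and 30%/12% rows, the attenuation is 0.028/0.50 = 6% to 0.123/0.50 = 25% of the assumed effect.

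6. One loss rule for both arms. If the arm rates are not fixed but follow from a common rule, loss of about 7%/3%, 13%/7% and 23%/13% gives attenuation of 0.011–0.029, 0.014–0.046 and 0.023–0.064 SD for ρ from 0.2 to 0.6.

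7. At the trial's size (165 vs 330, 3,000 simulated trials per case), mean estimate and 95% CI coverage are:

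- ρ 0.2, loss 10%/5%: −0.487, 94.6%
- ρ 0.4, loss 20%/8%: −0.446, 91.1%
- ρ 0.6, loss 30%/12%: −0.376, 77.5%
- ρ 0.6, loss 8%/15%: −0.549, 92.1%

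8. Remedy. Filling lost values by regression on arm, B, Z and the interactions of arm with B and Z, then fitting the same ANCOVA, leaves bias within 0.002 SD in every case. This tests bias only, not Rubin's variance, and by construction Z carries all the failure-related selection.

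9. Points scale. A separate simulation assumed a −4 point difference, residual SD 7, and loss of 20–35% on placebo and 8–15% on upadacitinib. The observed-case ANCOVA gave −2.99 to −3.69, full data −3.96 to −3.97, and imputation −3.93 to −3.96. That is an attenuation of about 0.3 to 1.0 points, or 0.3/7 = 0.04 to 1.0/7 = 0.14 SD, the same order as above.

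**The case against.** A reader might infer that the estimate is biased. The documents do not show that. Bias needs two things: a post-baseline course that predicts Week 12 SES-CD given arm and baseline, and selection that differs between arms. Neither quantity is given. If placebo loses more, the error understates the drug effect, which is conservative. This stands, and the conclusion has to be conditional.

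The design also limits loss. Stopping study drug does not by itself discard the endoscopy, and subjects who stop drug but stay in the study keep the visit schedule. Protocol Appendix C schedules an endoscopy at the premature discontinuation visit, although note f requires one only after 8 weeks. Part 3 is open only after the Week 12 endoscopy, with a COVID-19 exception, so failing placebo subjects have a reason to be scoped. A corticosteroid increase up to the baseline dose before Week 10 is not an intercurrent event. All this stands; it reduces failure-related loss but does not remove it.

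The version-history line may have meant COVID-19 missingness only. ANCOVA-C is not defined in the current SAP, and by analogy with NRI-C the suffix probably referred to COVID-19. On that reading the line is reasonable, but the SAP then gives no reason for dropping subjects lost for other causes.

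A reader might also infer that nothing in the plan could reveal a bias. That goes too far. SAP 9.2.3 offers tipping point analysis for continuous endpoints where appropriate and mentions ANCOVA in its steps, and SAP 9.5 analyses other endpoints along the lines of 9.4. But SAP 9.4.2 commits the analysis only to the continuous key secondary endpoints, FACIT-F and IBDQ. For SES-CD change it is possible, not promised.

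**Conclusion.** The point holds in conditional form. The MAR reason in the version history is too broad for a single-visit ANCOVA and does not cover failure-related loss that Week 2 to 8 data would predict. The SES-CD change estimate may be biased in either direction. The 0.03–0.12 SD attenuation rests wholly on the assumed loss rates and correlations. At 10%/5% loss it is 0.01–0.04 SD, and with balanced loss it is essentially nil.

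A reader might extend this to the confirmatory results. The documents do not support that: endoscopic response and endoscopic remission use NRI-C, IBDQ and FACIT-F use MMRM, and SES-CD change lies outside the testing hierarchy. Nor does the simulation support the same claim for CGHAS/IGHAS. Those scores come from an optional biopsy substudy of about 200 subjects and need separate consideration. This is an inexpensive improvement to a non-ranked endpoint, not a threat to the trial's main conclusions.

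**What to change.** In SAP 9.2.2, for change in SES-CD:

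- Run the same ANCOVA after multiple imputation under MAR. Impute Week 12 SES-CD from arm, strata, baseline SES-CD, age, gender, weight, SF, AP, CDAI and hs-CRP at Weeks 2, 4 and 8, and FCP at Week 4, using only values recorded before any intercurrent event. Combine by Rubin's rule.
- Keep the observed-case ANCOVA as a supplementary analysis, and state that it assumes missingness depends only on treatment, strata and baseline.
- State that the continuous tipping point analysis in 9.2.3 applies to SES-CD change. This covers loss that depends on unobserved values, which the imputation cannot correct.

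The cost is SAP wording and some extra modelling, including a choice of predictors, since CDAI already contains SF and AP. SAP 9.2.1 already plans PROC MI and Rubin's rule, and Appendix I would need one more seed. No new data are needed and no ranked endpoint changes.
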